Baseline Variables. To characterize the sample and explore potential moderators of treatment effectiveness, we will gather: additional demographics (student status, employment status); current ecigarette use and history (frequency and rate, 16,17 age of first use, motivation to quit and quitting history 18); nicotine dependence will be assessed with the Penn State Electronic Cigarette Dependence Index 19, EDS/PROMISE-E, 20 the Hooked on Nicotine Checklist, 21 and the E-cigarette Fagerström Test of Cigarette Dependence (e-FTCD) 22; other substance use (other tobacco products, alcohol) and mental health symptoms 23; and adverse childhood events. 24,25 For co-morbidities and adverse childhood events, we chose measures that are validated for use among adolescents. In order to minimize risk to participants, we deliberately avoided measures or deleted questions that assessed sensitive topics such as suicidality. Given evolving trends of e-cigarette use and perception, we will also ask about perception about harm from e-cigarettes, reasons for wanting to quit, and reasons for joining the study. To account for potential predictors of dropout, we will ask about motivation to use or quit e-cigarettes and potential barriers to quitting (e.g., social influences). We will assess baseline levels of perceived level of social support, 26,27 perceived social norms, and perceived self-efficacy for quitting and examine changes in these variables as potential mediators of treatment effectiveness.

Mediating Variables. We hypothesize that treatment engagement will mediate the relationship between treatment assignment and abstinence outcomes. We will extract data regarding replies to interactive text messages (e.g., setting a quit date, keyword use) as well as unsubscribe status, number of days enrolled, and total number of messages received. All text message interactions are date/time stamped.

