Missing Data. Missing data will be handled in two ways. First, we will conduct an intent-to-treat (ITT) analysis in which participants who have been lost to follow up are assumed to be treatment failures (i.e., vaping). This analysis will be conducted because ITT analyses are common in the smoking cessation literature, despite simulations demonstrating that the approach is neither conservative nor anti-conservative but rather biased in favor of whichever condition contains less missingness. Second, we will supplement the ITT analyses with an analysis that uses a multiple imputation (MI) procedure to minimize bias in estimates and standard errors, under the assumption that outcomes are not missing at random (NMAR) but rather more likely to be missing for treatment failures (i.e., vaping) than treatment successes (i.e. abstinence). Since the magnitude of actual response bias is unknown, we will conduct a sensitivity analysis to evaluate the treatment effect on outcomes under a range of magnitudes, from equal odds of missing (OR=1) to five times more likely to be missing (OR=5).

Mediator Analysis. Our conceptual model is that treatment increases the odds of abstinence by increasing perceived social support and perceived self-efficacy for quitting. Those two constructs will be measured at baseline, 1-month and 7-months post-treatment. Change in those constructs from baseline will be evaluated with separate mediation analyses as presented in Figure 1. Specifically, we hypothesize that the effect of treatment on abstinence will be mediated by perceived social support and perceived self-efficacy, such that: (1) a significant effect A is found associating X with Z; (2) a significant effect B is found associating Z with Y; (3) a significant effect C is found associating X with Y; and (4) the effect of C is significantly attenuated when A and B are simultaneously included in the model.

PROTECTION OF HUMAN SUBJECTS

Human Subjects Involvement, Characteristics, and Design

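### Separate mediation models for social support and self-efficacy can credit a construct that treatment shifts but that does not itself affect abstinence

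*Combined protocol and SAP*

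**What the plan says.** The Data Analysis Plan, under Mediator Analysis, sets out a conceptual model in which "treatment increases the odds of abstinence by increasing perceived social support and perceived self-efficacy for quitting". It then says that change from baseline in these two constructs will be "evaluated with separate mediation analyses as presented in Figure 1". Four conditions define mediation for each construct:

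- Criterion 1: "1) a significant effect A is found associating X with Z"
- Criterion 2: "2) a significant effect B is found associating Z with Y"
- Criterion 3: "3) a significant effect C is found associating X with Y"
- Criterion 4: "4) the effect of C is significantly attenuated when A and B are simultaneously included in the model"

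In criterion 4, A and B are the two paths of a single mediator, so its wording does not put the two constructs into one model. Under Measures, Baseline Variables, a third construct is added: the plan will assess "perceived social norms, and perceived self-efficacy for quitting and examine changes in these variables as potential mediators". Figure 1 is not reproduced in the text available, but the sentence that refers to it is explicit. No section adjusts one construct for another, states their expected correlation, or gives a significance level for these tests.

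**The concern.** The constructs are self-reported by the same participant at the same assessments, and the plan's own model has treatment raise both. Some correlation between the change scores is to be expected. If both shift with treatment, both pass criterion 1. Criterion 2 is the only step that looks at a construct's own link with abstinence, and in a one-at-a-time model that coefficient also picks up the effect of whatever correlated construct is left out. Criterion 3 is the same test whichever construct is examined, so it cannot tell them apart. Criterion 4 inherits the inflated B path.

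At stake is the interpretation of the secondary aim. The introduction says that results will be used to improve the programme. A construct that only accompanies the working mechanism could be taken for a mechanism.

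**Working it through.** The plan states no error rate, power or correlation for the mediation analysis, so there is no figure to reproduce. The check asks how often an inert construct Z2 meets all four criteria when only Z1 affects abstinence.

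**Inputs from the documents.** 900 per arm (Subjects). Expected follow-up of 75% at 1 month and 65% at 7 months (Potential Problems and Solutions), giving 0.75 × 1,800 = 1,350 in total and 0.65 × 900 = 585 per arm. Abstinence of 24.1% versus 18.6%, odds ratio 1.39, in the earlier young-adult trial (introduction).

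**Assumptions.** Two-sided 0.05 throughout, a Sobel test for criterion 4 (the plan names none), normal change scores with SD 1, a logistic outcome, and correlation ρ of 0.3, 0.5 or 0.7.

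- Setting A: n = 1,350; treatment shift 0.2 SD; Z1 effect 0.35 log-odds per SD; direct effect 0.26; intercept −1.5. The total effect is about 0.2 × 0.35 + 0.26 = 0.33 log-odds, and exp(0.33) = 1.39.
- Setting B: 900 or 585 per arm; shift 0.3 SD; Z1 effect 0.5 log-odds per SD; direct effect 0.19; calibrated to 18.6% versus 24.1%.

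**Mechanism.** With Z1 omitted, the B coefficient for Z2 is approximately ρ × b1. In setting A this is 0.3 × 0.35 = 0.105, 0.5 × 0.35 = 0.175 and 0.7 × 0.35 = 0.245, although the true value is 0.

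Criterion 1 depends on the shift in Z2. Its standard error in setting A is √(2/675) = 0.054. An equal shift of 0.2 gives z = 3.7. Under pure co-movement the shift is ρ × 0.2 = 0.06, 0.10 or 0.14, giving z = 1.1, 1.8 or 2.6. Criterion 1 therefore usually stops Z2 at ρ = 0.3 and often does not at 0.7.

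**Share of trials in which Z2 meets all four criteria**

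| Scenario | ρ = 0.3 | 0.5 | 0.7 | Joint model |
|---|---|---|---|---|
| A, equal shift | 14% | 38% | 59% | 0–2% |
| B, equal shift, 900 per arm | 55% | 79% | 81% | 3.1–3.7% |
| B, equal shift, 585 per arm | 28% | 57% | 63% | 2.0–2.3% |
| A, pure co-movement | 1% | 9% | 37% | 0–2% |
| Pure co-movement, 900 per arm* | 5–25% | 37–73% | 68–82% | 0–2% |
| Pure co-movement, 585 per arm* | 2–9% | 14–44% | 37–61% | 0–2% |
| A, equal shift, no direct effect | 2% | 4% | 6% | 0–2% |
| B, Z2 not shifted, 900 per arm | 0.6% | 1.7% | 3.3% | 0% |

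*Range over shifts of 0.2–0.3 SD and Z1 effects of 0.5–0.8 log-odds per SD.

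Another run at 900 per arm with strong effects and equal shifts gave 64%, 79% and 83%. Simulation error is about 1 point in the setting B rows, and repeats of setting A moved by up to about 4 points. With equal shifts and ρ = 0, setting B gives 2%, so correlation is what drives the excess.

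**Detection of the true mediator, separate versus joint.** In setting A at ρ = 0.7 it falls from about 66% to 58%. In the stronger settings it is nearly unchanged: 79–83% at 900 per arm and 57–65% at 585 per arm under either model.

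**The case against.** The strongest reply is that the plan's rule is stricter than it looks, and this stands in part. Criterion 3 caps every rate at the power for the total effect, about 81% at 900 per arm and 63% at 585. In setting A without a direct effect, the total effect is only about 0.07 log-odds. Criterion 3 then passes in roughly 8% of trials, and the inert construct is rarely declared. A reader who applied criteria 1 and 2 alone would infer far higher false-declaration rates, up to about 94% at correlation 0.7. That is not the planned rule, and the documents do not support it.

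Three other stronger readings also fail:

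- Correlation alone is not enough. A construct that treatment does not move is blocked by criterion 1.
- Adding the separate indirect effects would double-count, but the plan never proposes to add them.
- The secondary aim is to examine potential mediators. It does not promise to decide between them, and the conceptual model allows both to be real. The documents do not show that only one is.

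A last objection concerns the remedy. If one construct acts through the other, for example support raising self-efficacy, a joint model conditions on the downstream construct and understates the upstream one. This is correct, and it is a reason to show both sets of results. It is not a reason to rely on the separate models alone.

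**Conclusion.** The concern holds as a statement of what can happen under the written rule. It is not a prediction that it will happen. Separate models cannot distinguish a construct that carries the effect from one that shifts with treatment and is correlated with the carrier.

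With both constructs shifted equally and a total effect near an odds ratio of 1.39, the false-declaration rate at correlations 0.3, 0.5 and 0.7 is about 14%, 38% and 59% under modest effects. Under stronger effects at 900 per arm it is about 55–64%, 79% and 81–83%. The joint model gives about 1–4%. Pure co-movement at correlation 0.3 gives about 1–25%, and a small total effect keeps the rate at or below about 6%.

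Correlation, shifts and mediator effects are all assumed, because the documents give none. The primary abstinence comparison is unaffected. The consequence is limited to how the secondary aim is interpreted.

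**What to change.** Prespecify one outcome model in which all change-score mediators (social support, self-efficacy and, if it is kept, social norms) are entered together with treatment. Report each specific indirect effect and the joint indirect effect with bootstrap confidence intervals. Base any statement about which construct carries the effect on that model. Keep the one-at-a-time models alongside as descriptive, and say that the joint model may understate a construct that acts through another. Also state that the joint model still assumes no unmeasured confounding between mediators and outcome.

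The cost is analysis-plan wording, with no new data or participants. The statistical price is somewhat wider intervals when the constructs are highly correlated, as in the fall in detection at correlation 0.7 in setting A.

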The scientific, clinical, and public health communities are desperate for proven, evidence-based cessation resources to address the vaping epidemic among young people. We are uniquely positioned to address this urgent need given our extensive experience in conducting large-scale, rigorous research trials of digital tobacco cessation interventions and our expertise in working with young people. We plan to rapidly disseminate study results to benefit other researchers/service providers and use these results to further enhance the program.

METHODS

Subjects

We will randomize 1800 e-cigarette users aged 13-17 years old who are interested in quitting in the next 30 days to the two main intervention arms (900/arm). We will aim to randomize 450 to the waitlist control arm. Other eligibility criteria include past 30-day e-cigarette use and US residence. To fully enroll in the study, individuals must text a study-specific phone number and respond to the system-generated message.

Recruitment and Enrollment

Potential participants will respond to online ads on various social media platforms (Facebook, Instagram, etc.) if they are current e-cigarette users who are interested in quitting and willing to participate in a research study. Clicking on the ad will lead them to a webpage that provides details about what participation in the study entails and describes incentives for participation. Those who are interested will complete an eligibility screener followed by informed consent and a baseline assessment. Those who complete the baseline will be randomized into one of three arms (see below for additional details) and instructed to text a specific keyword corresponding to their treatment assignment to the same phone number. Only those who respond to the first message from the text message program within 24 hours will be fully enrolled into the study. This requirement will be made explicit.

Randomization

Randomization occurs after completion of the online enrollment process (completed baseline survey). A computer algorithm that is part of the survey software will automate random allocation.

Interventions

This is Quitting: Participants will be enrolled to receive messages from This is Quitting as described above.

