Assessment-only control: After an initial enrollment message, participants will be contacted monthly to assess e-cigarette use. At the end of the study, participants will receive information about how to sign up for This is Quitting if they are interested.

Waitlist control: After an initial enrollment message, participants will only be contacted at 1 and 7 months to complete the follow-up assessments; there will be no other contact via text message. At the end of the study, participants will receive information about how to sign up for This is Quitting if they are interested.

Potential Problems and Solutions

Loss to follow-up is the primary concern in trials involving digital interventions, especially ones that employ an assessment only or minimal contact controls. For the treatment and assessment only control arms, we expect at least 75% follow-up at 1-month and 65% at 7-months based on our previous and ongoing digital mobile-based evaluations. If follow-up rates are lower than expected early in the trial, we will consider shortening the 7-month follow-up to gather only abstinence outcomes.

To maximize follow up rates we will:

- 1) provide clear information about the study at the outset, including expectations for follow-up;
- 2) reimburse participants up to \$30 per follow-up assessment;
- 3) collect interim abstinence assessments via text ("Retention Messages": \$5 incentive for each response) for intervention and assessment-only control arms;
- 4) send reminders about follow-up surveys via email and text messages;
- 5) conduct phone follow-ups for those unreachable by email and text messages;
- 6) contact participants via social media private messaging function (if permission given); and,
- 7) emphasize the importance of survey completion regardless of abstinence status.

Conducting research online involving incentives carries the potential for fraud and participant deception as there are often no direct interactions with the participants.¹¹ To prevent fraudulent enrollments and participation from bots, we will utilize the following features on the Qualtrics survey platform:

- 1) Prevent multiple submission: Enabling this option allows Qualtrics to place a cookie on the browser the first time someone takes the survey. The user will be flagged as duplicate if they come back to take the survey from the same browser and device without having cleared their cookies.

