- 2) Bot detection: Enabling bot detection flags responses that are likely completed by bots by assigning a score to each response. This feature uses Google's invisible reCaptcha technology to assign a score to each response, with a score of less than 0.5 meaning that the respondent is likely a bot.
- 3) Relevant ID: This feature analyzes a user's browser, operating system, and location to calculate a fraud score that indicates whether the respondent is attempting to take the survey multiple times.

We also require a valid email address for completion of the baseline survey (users must click on a survey link in their email to launch the baseline and complete enrollment), which has been shown to prevent bots. ¹² We will monitor emails and phone numbers used to enroll in the study on a daily basis and exclude any duplicates. We anticipate these measures will prevent the majority of any potentially fraudulent enrollments.

Measures

All randomized participants in both arms will be asked to complete all assessments. Assessments will occur at baseline and 1 month and 7 months post-randomization. The baseline survey will be conducted online and hosted on a secure server. Mixed-mode follow-up (email, phone, text) will be employed. Telephone surveys will be conducted by research staff blind to treatment. Text messages have demonstrated moderately high reliability (k=.66) compared with web-based surveys in assessing smoking outcomes¹³ and will be used as a final means of gathering abstinence data from non-responders. Most measures listed below are standard instruments used in cessation studies, and are reliable when administered via the Internet. ^{14,15}

Screening Variables. Individuals located outside the U.S. (as determined by IP address captured by the survey platform) will be ineligible to participate. To characterize the sample of users interested in the study and assess study eligibility, we will gather: demographics (age, education, income level, sexual and gender identity, race, and ethnicity); current e-cigarette use (use of e-cigarette containing nicotine or THC in the past 30 days)¹⁶; interest in quitting; contact information (e-mail and phone number to send baseline survey to and link text message sign-up data). These questions are being asked during screening so we can determine whether enrolled participants are representative of the wider population of e-cigarette users.

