Step 1 (Study information): Potential participants who click on an online ad for e-cigarette users who are interested in quitting and willing to participate in a research study will be directed to a website that provide additional details about the study. This webpage will provide information on who is behind the study, what participation entails, and who may be eligible for the study. Step 2 (Eligibility screening): Individuals who are interested in participating will complete a short survey to confirm eligibility for study participation. Those who are eligible will be asked to provide contact information (e-mail address to send links to surveys and mobile number for text message sign up). Step 3 (E-mail confirmation): An email message is sent to the participant with a distinct URL (Web address) containing the baseline survey and instructions to complete the survey within 24 hours to complete study enrollment. This process ensures that enrolled participants have a valid email address where they can receive study-related correspondence. Step 4 (Informed consent): When the participant clicks on the URL in the email, it will open up an online baseline survey. On the first page of the baseline survey, the Informed Consent text will be provided, including a) each study condition; b) financial incentives for participating; c) the process of randomization and the equal chance of being assigned to one of three treatment conditions; d) protection of confidentiality and the right to withdraw at any time; and e) expectations regarding follow-up data collection, including compensation for time required to complete follow-up assessments (regardless of e-cigarette use status). Users will be required to select "Yes, I would like to continue" as active affirmation that they are providing consent for study participation. Contact information for the study and the Institutional Review Board where IRB approval has been obtained will be included in the Informed Consent form. All information about the study will be written at a 5th grade reading level to ensure adequate comprehension. Step 5 (Decisional capacity confirmation): After reading the informed consent, they will be asked to complete an assessment of decisional capacity and understanding of the informed consent by answering the following 7 questions:

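### No stated rule requires baseline answers to agree with the self-report screener on age and past-30-day vaping before a participant is randomized

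*Combined protocol and SAP*

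**What the plan says.** **Before screening.** Under Adequacy of Protection Against Risks, Step 1, the study webpage covers "what participation entails, and who may be eligible for the study". Recruitment and Enrollment adds that the page "describes incentives for participation".

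**Screening.** In Step 2, interested visitors "will complete a short survey to confirm eligibility for study participation". Measures, Screening Variables, lists "current e-cigarette use (use of e-cigarette containing nicotine or THC in the past 30 days" among the items gathered, with age and interest in quitting. One criterion does not depend on self-report: "Individuals located outside the U.S. (as determined by IP address captured by the survey platform) will be ineligible to participate".

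**Fraud checks.** Potential Problems and Solutions accepts that online research with incentives "carries the potential for fraud and participant deception". It lists a browser cookie, a bot score and a device-based fraud score. It adds a confirmed e-mail address and daily removal of duplicate e-mails and phone numbers. Item 3 of the Summary of Changes reports attention checks in the assessments, and consent wording that allows withdrawal of participants whose responses are flagged as possibly fraudulent.

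**Baseline and randomization.** Baseline Variables include frequency and rate of e-cigarette use, gathered to characterize the sample and "explore potential moderators of treatment effectiveness". Recruitment and Enrollment then says: "Those who complete the baseline will be randomized into one of three arms". Step 7 limits randomization to eligible participants who have confirmed eligibility, consented, passed the capacity questions and completed the baseline.

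**Outcome.** The primary outcome is self-reported 30-day abstinence at 7 months. Under Missing Data, the intention-to-treat analysis counts those lost to follow-up as vaping.

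**The concern.** The listed checks ask whether a respondent is a bot, has been here before, or gives responses that look fraudulent. The documents describe none as asking whether a real person, entering once, is aged 13 to 17 and vapes. Two facts make this matter for the primary analysis.

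First, the outcome is self-reported, with no verification described. A non-vaper who truthfully reports no vaping at 7 months is scored as a success in whichever arm they were placed.

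Second, all payment depends on follow-up. Payment for participation gives nothing for enrollment or baseline and up to 95 dollars afterwards in the two main arms. Someone who entered for the money has a reason to respond.

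The result would be a higher abstinence rate in every arm and a smaller contrast. The waitlist arm would not separate this from genuine quitting, because all three arms pass through the same screener. Meanwhile, an inexpensive signal goes unused: the baseline asks about frequency of use just before randomization, and the plan states no comparison with the screener.

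**Working it through.** **Inputs from the documents**
- Abstinence of 24.1% (intervention) and 18.6% (assessment-only control), from the young adult trial in the background section.
- 900 per main arm (Subjects).
- Expected 7-month follow-up of at least 65% in the two main arms (Potential Problems and Solutions).
- Payments: two surveys at up to 30 dollars and seven texts at 5 dollars. 2 × 30 + 7 × 5 = 95 dollars, as stated. Waitlist participants receive no text payments, so their maximum is 60 dollars.

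**Assumptions**
- Two-sided 5% test. The protocol refers to sample size calculations but does not show alpha, power or target effect.
- f, the share of false entrants, equal in both arms because of randomization: 5% and 10%.
- q, the chance that a false entrant is counted abstinent: 0 (all lost or reporting vaping), 0.65 (all respond at the planned rate and report abstinence) or 1.

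**Base case.** The 900 per arm cannot be strictly reproduced without its inputs. With 24.1% against 18.6%, 80% power needs 871 per arm, so 900 is consistent with that target. Power at n per arm is

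Φ{ [d − 1.96 √(2p̄(1−p̄)/n)] / √([p₁(1−p₁)+p₂(1−p₂)]/n) }.

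Here d = 0.055, p̄ = 0.2135 and n = 900. The numerator is 0.055 − 1.96 × 0.01932 = 0.01714, the denominator is 0.01927, the ratio is 0.889 and power is 81.3%. The odds ratio is (0.241/0.759)/(0.186/0.814) = 1.39, matching the protocol's figure.

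**With false entrants.** Observed rate = (1 − f) × true rate + f × q. For f = 10% and q = 0.65:
- Intervention: 0.90 × 0.241 + 0.10 × 0.65 = 0.2819.
- Control: 0.90 × 0.186 + 0.10 × 0.65 = 0.2324.
- Odds ratio: (0.2819/0.7181)/(0.2324/0.7676) = 1.30.
- Power: (0.0495 − 1.96 × 0.02060)/0.02057 = 0.443, giving 67.1%.

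| f | q | Intervention | Control | Difference (points) | Odds ratio | Power |
|---|---|---|---|---|---|---|
| 0 | – | 24.1% | 18.6% | 5.5 | 1.39 | 81.3% |
| 5% | 0 | 22.9% | 17.7% | 5.2 | 1.38 | 78.8% |
| 5% | 0.65 | 26.1% | 20.9% | 5.2 | 1.34 | 74.3% |
| 5% | 1 | 27.9% | 22.7% | 5.2 | 1.32 | 72.3% |
| 10% | 0 | 21.7% | 16.7% | 5.0 | 1.38 | 76.0% |
| 10% | 0.65 | 28.2% | 23.2% | 5.0 | 1.30 | 67.1% |
| 10% | 1 | 31.7% | 26.7% | 5.0 | 1.27 | 63.7% |

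The difference shrinks by the factor (1 − f) whatever q is. When q exceeds the true rates, both arms' rates also rise and power falls further.

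**Direction.** With equal retention of false entrants, the bias is toward no effect. If their retention differed between arms by 10 points (an assumption) and those retained reported abstinence, f = 10% would add 0.10 × 0.10 = 1.0 point, in either direction.

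**The case against.** The plan does more than block bots and duplicates. Location is checked by IP address, attention checks were added, and flagged participants may be withdrawn. Nothing is paid at enrollment or baseline. Entrants must also answer the capacity questions correctly and respond by text within 24 hours. A reader might infer that a false entrant meets no other obstacle, and the documents do not support that. But none of these steps is described as checking age or vaping: the capacity questions test understanding of the study, and the text step tests reachability. Withdrawal comes after enrollment, so it is no substitute for a check made before randomization.

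A reader might also infer that someone with contradictory answers is certain to be randomized. The documents do not say so. Step 7 speaks of eligible participants who have confirmed eligibility and is silent on discordance. The supportable statement is that no rule is given.

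Nor does every false entrant become a quitter. They must finish text sign-up, respond at 7 months and report abstinence. Non-response counts as vaping, payment does not depend on the answer, and someone who misstates only age may be a real vaper. The q = 0 rows show this milder case.

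The strongest objection concerns the remedy. An agreement rule stops only people who contradict themselves, and their share is unknown. That stands, so the power table cannot be read as the gain from the fix.

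**Conclusion.** The concern holds in limited form. Age and past-30-day vaping rest on self-report given after a page that says who may be eligible and describes incentives. No described check tests either, and no rule requires screener and baseline to agree before randomization.

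Under the stated assumptions, power falls from 81% to 72–74% with 5% false entrants and to 64–67% with 10%, if all or 65% of them are counted abstinent. At 10% with none counted abstinent, it is 76%. The false-entry share is assumed, and these are total losses from false entry.

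Two further readings are tempting but unsupported. The protocol mentions relatively high control quit rates in the young adult trial, but ties them to assessment reactivity and retention incentives, not false entry. If false entry did contribute to the 18.6%, adding f on top would partly double-count it. Nor does this build in an advantage for the intervention: with equal retention, the effect is dilution. The change is still worth making, because the base case has little power to spare and the cost is small.

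**What to change.** **Main change.** Before the randomizer runs, require the baseline past-30-day use item to be above zero and a re-asked age item (for example, birth month and year) to agree with the screener. Do not randomize discordant entries. State the rule under Randomization and in Step 7. The use item should have the same scope as the screener, which counts nicotine or THC, so that eligible users are not rejected by a narrower question. The baseline is to be completed within 24 hours of the e-mailed link, so true status should rarely change in between.

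**Secondary step.** Keep the landing page general and do not state exact qualifying thresholds. The documents do not say that the page now shows the exact age range, the 30-day rule or the 95-dollar total, so this may need little or no change. The gain is probably modest, since the ads already address e-cigarette users who want to quit.

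**Cost.** Survey logic and possibly some web text. A few genuine participants with inconsistent answers would be lost. Because this happens before randomization, it does not bias the arm comparison and needs no later exclusions. Entrants who misstate consistently will still pass.
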